#### 6.3.1.14 Dose modification and management guideline for hemorrhage

Hemorrhage, including major hemorrhage defined as symptomatic bleeding in a critical area or organ, can occur when dabrafenib is administered with trametinib. Permanently discontinue dabrafenib and trametinib for all Grade 4 hemorrhagic events and for any persistent Grade 3 hemorrhagic events. Withhold dabrafenib and trametinib for Grade 3 hemorrhagic events; if improved, resume at the next lower dose level.

# 6.3.1.15 Dose modification and management guideline for thromboembolic events

Advise patients to immediately seek medical care if they develop symptoms of DVT or pulmonary embolism (PE), such as shortness of breath, chest pain, or arm or leg swelling. If any signs or symptoms of venous thromboembolism are present, the patient will undergo specific laboratory and medical imaging assessments to confirm. The medical imaging assessment(s) selected will depend on the anatomic site or organ of involvement. If the diagnosis is confirmed, appropriate medical care according to standard local clinical practice should be initiated immediately.

Permanently discontinue trametinib for life threatening PE. Withhold trametinib for uncomplicated venous thromboembolism for up to 3 weeks; if improved, trametinib may be resumed at a lower dose level. Dabrafenib dosing may continue.

# 6.3.1.16 Dose modification and management guidelines for carboplatin with vincristine treatment

The induction cycle should only be interrupted in the event of grade 3 neurotoxicity, grade 2 nephrotoxicity, grade 4 hematologic toxicity, or disease progression.

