  - Platelets ≥75,000/μL and transfusion independent, defined as not receiving platelet transfusions within a 7 day period prior to meeting this enrollment criteria. Note for LGG patients only, platelets ≥ 100,000/μL prior to Day 1 dosing.
  - Hemoglobin  $\geq 8.0$  g/dL (may receive red blood cell transfusions)
- 10. Adequate renal function defined as:
  - Calculated eGFR (Schwartz formula) or radioisotope GFR ≥90 mL/min/1.73 m^2; or

- A serum creatinine within the testing lab reference range (for age/gender, if available)
- 11. Adequate liver function defined as:
  - Total Bilirubin (sum of direct and indirect)  $\leq 1.5$  x upper limit of normal (ULN) for age except for subjects with Gilbertsyndrome who may only be included if the total bilirubin is  $\leq 3.0$  x ULN or direct bilirubin  $\leq 1.5$  x ULN
  - AST and ALT ≤2.5 x ULN
- 12. Adequate cardiac function defined as:
  - LVEF greater than or equal to institutional LLN by ECHO (while not receiving medications for cardiac function)
  - Corrected QT (QTcF) interval ≤480 msecs.
- 13. If receiving glucocorticoids, patient must be on a stable or weaning dose for at least 7 days prior to the first dose of study treatment.
- 14. Written informed consent/assent must be obtained prior to any protocol specific screening procedures being performed.

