## 6.1.2.1 Induction Therapy

Prior to induction, central or local lab results must be assessed to confirm ANC  $\geq 1000/\mu L$  and platelet count  $\geq 100,000/\mu L$ .

Induction will consist of 10 weeks of therapy followed by 2 weeks without chemotherapy. Induction should only be interrupted in the event of grade 3 neurotoxicity, grade 2 nephrotoxicity, grade 4 hematologic toxicity, or disease progression. See Section 6.3.1.16 for dose modification guidelines.

Carboplatin (CBDCA): 175 mg/m^2 as weekly IV infusion over 60 minutes on weeks 1 to 4, and on weeks 7 to 10, on the same day as VCR dosing

Vincristine (VCR): 1.5 mg/m^2 as weekly IV bolus infusion (0.05 mg/kg if child is <12 kg) (maximum dose of 2.0 mg) for 10 weeks.

Table 6-9 Induction therapy

| Week
1 | Week
2 | Week
3 | Week
4 | Week
5 | Week
6 | Week
7 | Week
8 | Week
9 | Week
10 | Week
11 | Week
12 |
|-----------|-----------|-----------|-----------|-----------|-----------|-----------|-----------|-----------|------------|------------|------------|
| VCR        | Rest       | Rest       |
| CBDC      | CBDC      | CBDC      | CBDC      |           |           | CBD       | CBDC      | CBDC      | CBDC       |            |            |
| Α         | Α         | Α         | Α         |           |           | CA        | Α         | Α         | Α          |            |            |

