#### 6.3.1.2 Renal Insufficiency

Cases of renal insufficiency have occurred in adult patients receiving dabrafenib and the combination of dabrafenib and trametinib. Prior to start of study treatment, concomitant medications must be reviewed for the potential risk of inducing nephrotoxicity and concomitant medications may be modified if clinically possible.

Guidelines regarding management and dose reduction for renal insufficiency considered to be related to study treatment by the investigator are provided Table 6-17.

Table 6-17 Mandatory dose modifications and recommended clinical management guidelines for renal function alterations

| NCI-CTCAE v4.03                          |  |  |
|--|--|--|
| Grade                                    | Recommended adverse event
management guidelines   | Mandatory dose modification requirements   |
| Grade 1 (Creatinine > ULN to ≤ 1.5× ULN) | 
 
Monitor creatinine weekly
 
If creatinine return to baseline resume routine creatinine monitoring per protocol
 
Promote hydration and cessation of nephrotoxic drugs.
 
 | Continue dabrafenib and trametinib at the same dose.   |
| Grade 2 (Creatinine > 1.5× to ≤ 3× ULN   | 
 
Monitor creatinine every 2 to 3 days
 
Consult with specialist and consider renal biopsy
 
Promote hydration and cessation of nephrotoxic drugs.
 
                       | 
 
Interrupt dabrafenib and trametinib until ≤ Grade 1 or baseline and then reinstate dabrafenib and trametinib at the same dose.
 
2nd occurrence:         
 
Interrupt dabrafenib and trametinib until ≤ Grade 1 or baseline. Once recovered, reduce dabrafenib and trametinib to the next dose level. Re-escalation of the patient's dose is recommended if criteria in Section 6.3.1 are met.
 
 
 
3rd occurrence:         
 
Interrupt dabrafenib and trametinib until ≤ Grade 1 or baseline. Once recovered, reduce dabrafenib and trametinib to the next dose level. Re-escalation of the patient's dose is recommended if criteria in Section 6.3.1 are met.
 
 
 
4th occurrence         
 
Permanently discontinue dabrafenib and trametinib.
 
 
 
 |

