#### 6.3.1.16.2 Nephrotoxicity

If creatinine is greater than upper limit of normal for the patient's age, a creatinine clearance or GFR must be determined. If the creatinine clearance is <75% of normal for the patient's age, then the carboplatin dose should be held until creatinine clearance recovers to 75% of normal. Carboplatin dose should then be reduced by 25%.

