#### 6.3.1.16.4 Neurotoxicity

#### Seizures

**Novartis** 

For seizure due to vincristine, hold one dose, then resume at 1.0 mg/m^2 (1.5 mg max) while on anticonvulsants. If seizures do not recur, escalate to full dose. For seizures not associated with vincristine, place patient on anticonvulsants after appropriate neurological evaluations, and proceed with chemotherapy at full doses.

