#### **Encephalopathy**

Neither carboplatin nor vincristine commonly cause encephalopathy. Therefore the patient must be carefully assessed for other causes including hydrocephalus, shunt malfunction, overhydration, too rapid withdrawal of steroids, syndrome of inappropriate antidiuretic hormone secretion (SIADH), hypothalamic dysfunction, hemorrhage, anticonvulsant toxicity, etc. If a correctable cause cannot be identified, delay therapy up to 2 weeks and proceed only if patient has improved substantially. Proceed with 20% reduction of both carboplatin and vincristine.

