# 8 Safety monitoring and reporting

### 8.1 Adverse events

# 8.1.1 Definitions and reporting

An adverse event is defined as the appearance of (or worsening of any pre-existing) undesirable sign(s), symptom(s), or medical condition(s) that occur after patient's signed informed consent/assent has been obtained.

Abnormal laboratory values or test results occurring after informed consent constitute adverse events only if they induce clinical signs or symptoms, are considered clinically significant, require therapy (e.g., hematologic abnormality that requires transfusion or hematological stem cell support), or require changes in study medication(s).

Adverse events that begin or worsen after informed consent should be recorded in the Adverse Events CRF. Conditions that were already present at the time of informed consent should be recorded in the Medical History page of the patient's eCRF. Adverse event monitoring should be continued for at least 30 days following the last dose of study treatment. Adverse events (including lab abnormalities that constitute AEs) should be described using a diagnosis whenever possible, rather than individual underlying signs and symptoms. When a clear diagnosis cannot be identified, each sign or symptom should be reported as a separate Adverse Event.

Adverse events will be assessed and graded according to the Common Terminology Criteria for Adverse Events (CTCAE) version 4.03. Grade 1 to 5 will be used to characterize the severity of the Adverse Event.

If CTCAE grading does not exist for an adverse event, the severity of mild, moderate, severe, and life-threatening, death related to the AE corresponding respectively to Grades 1 - 5, will be used. Information about any deaths (related to an Adverse Event or not) will also be collected though a Death form.

The occurrence of adverse events should be sought by non-directive questioning of the patient (subject) during the screening process after signing informed consent/assent and at each visit during the study. Adverse events also may be detected when they are volunteered by the patient (subject) during the screening process or between visits, or through physical examination, laboratory test, or other assessments. As far as possible, each adverse event should be evaluated to determine:

- 1. The severity grade (CTCAE Grade 1-5)
- 2. Its duration (Start and end dates)

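### Induction chemotherapy may 'only' be interrupted for four listed events, yet the same section orders an ungraded delay for encephalopathy and a carboplatin hold that can apply at grade 1 creatinine

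*Protocol*

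**What the plan says.** Section 6.1.2.1, on the 10-week induction course, states: "Induction should only be interrupted in the event of grade 3 neurotoxicity, grade 2 nephrotoxicity, grade 4 hematologic toxicity, or disease progression". It then refers to Section 6.3.1.16 for dose modification. That section opens with the same restriction: "The induction cycle should only be interrupted in the event of grade 3 neurotoxicity, grade 2 nephrotoxicity, grade 4 hematologic toxicity, or disease progression".

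The subsections that follow give organ-specific rules:

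- **Section 6.3.1.16.2 (nephrotoxicity).** Creatinine above the upper limit for age requires a clearance or GFR. Then: "If the creatinine clearance is <75% of normal for the patient's age, then the carboplatin dose should be held". The hold lasts until clearance is back to 75% of normal, and carboplatin is then cut by 25%. No grade is named.
- **Section 6.3.1.16.4 (encephalopathy).** "If a correctable cause cannot be identified, delay therapy up to 2 weeks and proceed only if patient has improved substantially". Both drugs then restart with a 20% reduction. No grade is named.

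Neither rule is limited to one phase. Sections 6.3.1.16.1 and 6.3.1.16.3 do name the phase they cover.

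On grading, Section 8.1.1 says: "Adverse events will be assessed and graded according to the Common Terminology Criteria for Adverse Events (CTCAE) version 4.03". Section 6.3.1 applies the same version to dose modifications. Table 6-17 (Section 6.3.1.2), labelled with that version, begins with "Grade 1 (Creatinine > ULN to ≤ 1.5× ULN" and places grade 2 above 1.5 and up to 3 x ULN.

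**The concern.** The word 'only' turns the four events into a closed list, and no sentence ranks that list against the subsections beneath it. The cross-reference in 6.1.2.1 does not help, because 6.3.1.16 opens with the same list.

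A site that follows the list literally would keep dosing through encephalopathy below grade 3, and would keep giving carboplatin at a grade 1 creatinine even with clearance under 75% of normal. A site that follows the subsections would hold. Two children with the same findings could be managed differently under one protocol, and the literal reading is the less safe one.

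**Working it through.** This is mainly a comparison of texts, with one line of arithmetic for the renal rule. The plan states no figure to reproduce.

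**1. Do the two subsections apply during induction?** Section 6.3.1.16.3 limits its hold to maintenance, and 6.3.1.16.1 names both induction and maintenance. The renal and encephalopathy rules name no phase, so they apply in both.

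**2. Encephalopathy.** The list requires grade 3 neurotoxicity. Section 6.3.1.16.4 delays therapy as a whole at any grade when no correctable cause is found, and both drugs are reduced on restart. Below grade 3 the two instructions cannot both be followed. This does not depend on what counts as an interruption.

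**3. Renal.** Inputs: hold at clearance below 75% of normal once creatinine exceeds ULN (6.3.1.16.2); grade 1 is above 1.0 and up to 1.5 x ULN, and grade 2 starts above 1.5 x ULN (Table 6-17). Assumption: clearance is inversely proportional to creatinine, as in the creatinine-based estimate named in Section 5.2 ("Calculated eGFR (Schwartz formula) or radioisotope GFR").

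Let r be the creatinine, in multiples of ULN, at which the child's clearance is normal for age, and c the current creatinine in the same units. Clearance as a fraction of normal is r/c. The hold applies when c > 1 and r/c < 0.75, so it starts at the larger of 1 and r/0.75.

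- r = 1.0 (the highest value considered): 1/0.75 = 1.33 x ULN.
- r = 0.9: 0.9/0.75 = 1.20 x ULN.
- r = 0.75 or lower: as soon as creatinine exceeds ULN.

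At the top of grade 1 with r = 1.0, clearance is 1/1.5 = 66.7% of normal, already below 75%. The documents do not give r; the range up to 1.0 is assumed. Throughout it the hold starts below the 1.5 x ULN line for grade 2.

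**4. Is a carboplatin hold an interruption?** The protocol does not define the term. Grade 4 hematologic toxicity is on the list, yet 6.3.1.16.1 says vincristine is not held for myelosuppression once a phase has started. On that sentence, the listed hematologic interruption is itself a hold of carboplatin alone. But the same subsection also tells sites to hold chemotherapy as a whole when counts fall. The evidence favours counting a one-drug hold, without settling it.

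**5. Size of the arm.** 102 x 1/3 = 34 control children. At Amendment 5, 44 LGG patients had been randomized, leaving 102 - 44 = 58, of whom about 58/3 = 19 would still enter this arm. No event rates are given, so the number of children affected cannot be calculated.

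**The case against.** The strongest reply is that specific rules sit directly under the general sentence, and a sensible reader lets the specific rule govern. On the renal rule, the list speaks of interrupting the cycle, while 6.3.1.16.2 holds one drug and leaves weekly vincristine running. Grade 2 nephrotoxicity is not defined for this arm; Table 6-17 was written for dabrafenib with trametinib; and 6.3.1.16.2 allows a measured GFR, which need not track creatinine exactly. On encephalopathy, the topic falls under neurotoxicity, which is a listed category, and the protocol itself says neither drug commonly causes it.

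Much of this stands as a limit on size. It is why the renal conflict is conditional and the encephalopathy conflict narrow. It does not reconcile the text: 'only' is written twice, and nothing tells the site which instruction prevails. Table 6-17 carries the CTCAE version that Section 6.3.1 sets for dose modifications, so it is the best scale the protocol offers.

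A reader might infer more than the documents support:

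- **That the protocol forces unsafe dosing.** It does not. Section 6.1.6 lets treatment stop for unacceptable toxicity or at the investigator's discretion, and 6.1.2 also requires local labels to be followed.
- **That the vincristine holds in 6.3.1.16.4 are further conflicts.** The seizure rule reads "For seizure due to vincristine, hold one dose, then resume at 1.0", and the neuropathy rule is similar. Both hold vincristine alone, so they conflict only if a one-drug hold is an interruption.
- **That hepatotoxicity is a contradiction.** The hold in 6.3.1.16.3 covers maintenance, and the induction list omits hepatotoxicity, so the two agree. What remains is a possible gap for an isolated grade 3-4 liver abnormality in induction, partly covered by local labels, investigator discretion and the drug-induced liver injury rule in 6.3.1.17.

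**Conclusion.** The wording is wrong as it stands, and the correction is minor. The encephalopathy conflict is direct for any event below grade 3. The renal conflict is well supported but rests on three things: a carboplatin hold counting as an interruption, the grade bands of Table 6-17 applying to this arm, and clearance being roughly inverse to creatinine with normal clearance at or below ULN. Given these, the hold starts at about 1.33 x ULN or lower, before the grade 2 line of 1.5 x ULN.

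The consequence is a patient-safety instruction open to two readings during one 10-week course in about 34 children. It has no bearing on the ORR comparison, power or alpha.

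**What to change.** In both 6.1.2.1 and 6.3.1.16, replace 'only' with wording such as 'except as directed in Sections 6.3.1.16.1 to 6.3.1.16.5 and 6.3.1.17'. In 6.3.1.16.1, make the hold for low counts name carboplatin rather than chemotherapy, to match the sentence that keeps vincristine going through myelosuppression.

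As a suggestion only, the sponsor should confirm whether the grade 3-4 hepatotoxicity hold is meant to exclude induction, and say so either way.

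The cost is amendment wording and a notice to sites. No assessments are added: Table 7-3 already schedules chemistry at weeks 1, 2, 3, 4, 5 and 8 of induction.

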#### 6.3.1.16.1 Myelosuppression

To begin induction or each cycle of maintenance chemotherapy:

• ANC should be  $\geq 1000/\mu L$  and platelet count  $\geq 100,000/\mu L$ 

If ANC  $<1,000/\mu$ L or platelet count  $<100,000/\mu$ L:

• hold administration and repeat counts every 7 days.

Each cycle of induction or maintenance chemotherapy should begin at full dose, unless delays have been required because of myelosuppression during the previous two successive cycles. If this has occurred, then begin the next cycle with 75% of full dose carboplatin.

During induction or maintenance:

- If ANC falls  $<500/\mu L$  and/or platelet count  $<50,000/\mu L$ , hold chemotherapy administration and repeat counts every 7 days until they recover to an ANC of  $\ge 1000/\mu L$  and platelet count of  $\ge 100,000/\mu L$ .
- Resume at 75% of full dose carboplatin when these levels are reached. The 75% reduced dose should continue for the remainder of Induction or Maintenance.

However, if a patient is dose reduced during Induction, they can start the first maintenance cycle at 100% dosing. Those patients who are dose reduced during maintenance, should continue at the dose reduction throughout the remainder of all maintenance cycles.

Once induction or maintenance has started, vincristine should not be held due to Myelosuppression.

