## 6.1.2.2 Maintenance Therapy

Following induction therapy and two weeks of rest, maintenance therapy should begin if peripheral counts recover to ANC  $\geq 1,000/\mu L$  and platelet count  $\geq 100,000/\mu L$ . Repeat blood counts every 7 days until counts are adequate. Recovery of peripheral counts is required prior to starting each maintenance cycle. Local laboratory results may be used prior to dosing if a central lab is not scheduled per protocol or when central lab results will not available in time for a scheduled cycle. Results will be collected in the eCRF.

Each maintenance cycle will be 6 weeks in duration and consists of 4 weekly doses of carboplatin, and three weekly doses of vincristine given concomitantly with the first 3 weeks of carboplatin, followed by two weeks of rest. Maintenance will continue for a total of 8 cycles. See Section 6.3.1.16 for dose modification guidelines.

Carboplatin (CBDCA): 175 mg/m^2 as weekly IV infusion over 60 minutes on weeks 1 to 4 of each cycle.

Vincristine (VCR): 1.5 mg/m^2 as weekly IV bolus infusion (0.05 mg/kg if child is <12 kg) (maximum dose of 2.0 mg) on weeks 1 to 3 of each cycle, on the same day as CBDCA dosing.

Table 6-10 Maintenance therapy

| Week 1 | Week 2 | Week 3 | Week 4 | Week 5 | Week 6 |
|--------|--------|--------|--------|--------|--------|
| VCR    | VCR    | VCR    |        | Rest   | Rest   |
| CBDCA  | CBDCA  | CBDCA  | CBDCA  |        |        |

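### The control-arm myelosuppression rules conflict on whether vincristine is held, and do not agree on the carboplatin dose that opens the next maintenance cycle

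*Protocol*

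**What the plan says.** All of this is current protocol text for the LGG control arm.

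- **In-course hold (6.3.1.16.1).** If ANC falls below 500/µL and/or platelets below 50,000/µL during induction or maintenance, sites are to "hold chemotherapy administration and repeat counts every 7 days until they recover" to an ANC of at least 1,000/µL and platelets of at least 100,000/µL. Carboplatin then resumes at 75%.
- **Vincristine (6.3.1.16.1, last line).** "Once induction or maintenance has started, vincristine should not be held due to Myelosuppression".
- **Start of a cycle (6.1.2.2).** "Recovery of peripheral counts is required prior to starting each maintenance cycle". Section 6.3.1.16.1 likewise asks for recovered counts before induction and before each maintenance cycle, and for administration to be held otherwise.
- **Carboplatin dose at the start of a cycle (6.3.1.16.1).** The one exception looks back over two cycles: "Each cycle of induction or maintenance chemotherapy should begin at full dose, unless delays have been required because of myelosuppression during the previous two successive". In that case the next cycle begins at 75%.
- **Carboplatin dose after an in-course reduction (6.3.1.16.1).** The 75% dose lasts for the rest of the phase. A child reduced in induction may start maintenance at full dose, whereas children reduced in maintenance "should continue at the dose reduction throughout the remainder of all maintenance cycles".

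**The concern.** The first two rules cover the same period and the same toxicity, and give opposite instructions for vincristine. The last line is not worded as an exception to the hold, and the hold names no drug that it spares. The start-of-cycle requirement repeats the problem. At cycles 2 to 8 the maintenance phase has already started and vincristine is due in week 1, yet the cycle may not begin until counts recover.

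The carboplatin rules disagree in a smaller way. The full-dose sentence applies to each cycle and names a single exception. A child with one mid-cycle hold in maintenance, and no delay in the cycle before, falls outside that exception but inside the sentences that make the reduction last.

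At stake is what a child in the randomised control arm receives at low counts. Vincristine is either given or withheld during deep cytopenia, and the following maintenance cycle opens at either 100% or 75% carboplatin. Section 12 permits no authorised deviations, so a site that obeys one sentence departs from another.

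**Working it through.** The protocol states no figure on this point, so there is nothing to reproduce. The check has two parts: what the words mean, then how far apart the carboplatin readings are.

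**1. Which drugs does a hold of chemotherapy cover?**

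- Section 6.1.2 describes carboplatin and vincristine together as the chemotherapy of induction and maintenance.
- Section 6.3.1.16.3 (hepatotoxicity) orders chemotherapy held, then reduces both drugs by 25% if the cause is unexplained. There the word covers both.
- Section 6.3.1.16.2 (nephrotoxicity) names carboplatin alone when only carboplatin is to be held.
- Section 6.1.2.2 places maintenance vincristine on the same day as carboplatin. Giving vincristine while carboplatin is held therefore also sits awkwardly with the schedule.

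On the protocol's own usage, the in-course hold includes vincristine and the last line of 6.3.1.16.1 excludes it. Planned vincristine doses are 10 (induction) + 8 × 3 (maintenance) = 34. Counts are repeated every 7 days during a hold, so each weekly recount can mean one of those doses is given or omitted.

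**2. How far apart are the two carboplatin readings?**

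Inputs (6.1.2.1, 6.1.2.2): 175 mg/m² per dose; 8 induction doses (weeks 1 to 4 and 7 to 10); 8 maintenance cycles of 4 doses.

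- Induction: 8 × 175 = 1,400 mg/m².
- Maintenance: 8 × 4 × 175 = 5,600 mg/m².
- Planned total: 1,400 + 5,600 = 7,000 mg/m².
- One in-course hold in maintenance cycle k, no other modification. Gap over the later cycles = 0.25 × (8 − k) × 4 × 175 mg/m².

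| Hold in maintenance cycle | Later cycles at full dose (mg/m²) | Later cycles at 75% (mg/m²) | Gap (mg/m²) | Gap as % of 5,600 | Gap as % of 7,000 |
|---|---|---|---|---|---|
| 1 | 4,900 | 3,675 | 1,225 | 21.9 | 17.5 |
| 4 | 2,800 | 2,100 | 700 | 12.5 | 10.0 |
| 7 | 700 | 525 | 175 | 3.1 | 2.5 |

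The cycle 1 row is the worst case. The gap falls by 175 mg/m² for each cycle the hold comes later.

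**3. How much of this can accrue by the primary analysis?**

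The primary analysis waits until every patient has completed 32 weeks of treatment or stopped earlier (4.1). Induction takes 12 weeks and each maintenance cycle 6, so without delays week 32 is the second week of maintenance cycle 4 (12 + 3 × 6 = 30). For a patient with only that minimum follow-up, the later doses after a cycle 1 hold number 4 + 4 + 2 = 10. The gap is then at most 10 × 43.75 = 437.5 mg/m². Patients enrolled earlier can have more.

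**The case against.** The best defence reads section 6.3.1.16.1 in order and lets the later, more specific lines govern. After the in-course hold, only carboplatin is given a resumption dose, and the closing line then exempts vincristine. The start-of-cycle rule concerns a cycle not yet begun. For carboplatin, two explicit sentences keep the child at 75%, so a full-dose restart would mean ignoring both in favour of an earlier general sentence.

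Much of this stands for carboplatin. The carry-over is expressly addressed, and the fault is a general sentence that lacks a second exception. That is why the point is secondary and 1,225 mg/m² is only an upper limit. It stands less well for vincristine. The protocol does not say that the last line qualifies the hold, its usage elsewhere makes the hold cover both drugs, and whether maintenance having started refers to the phase or the cycle is left open. Section 4.1 also has the regimen followed alongside institutional practice. That accepts some variation between sites, but it does not choose between opposite instructions.

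A reader might also infer a third contradiction. Section 6.3.1.16 says "The induction cycle should only be interrupted in the event of grade 3 neurotoxicity, grade 2 nephrotoxicity, grade 4 hematologic toxicity, or disease progression", while the encephalopathy rule says "If a correctable cause cannot be identified, delay therapy up to 2 weeks". The documents do not support calling that reason unlisted. The encephalopathy rule sits under the Neurotoxicity heading (6.3.1.16.4), and grade 3 neurotoxicity is on the list. It also has nothing to do with myelosuppression.

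**Conclusion.** The point holds as a conflict in operative dosing text. The main defect is vincristine: section 6.3.1.16.1 both holds it, as part of chemotherapy, and forbids holding it at the same low counts, and the start of cycles 2 to 8 raises the same question. The secondary defect is the full-dose sentence, whose one exception does not cover a child already reduced in maintenance. The carboplatin readings differ by 175 to 1,225 mg/m² for holds in cycles 7 to 1 (2.5% to 17.5% of the planned 7,000), assuming one hold and no other change.

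The consequence is that a control child who meets a count threshold can be treated differently depending on the sentence a site follows. A reader might go further and infer that many of the roughly 34 controls (102 ÷ 3) will be affected and that control ORR, PFS or power will shift. The document does not support this. Section 2.1 lists hematologic suppression as a toxicity without a rate, no rate is given for either count threshold, and nothing links dose intensity to response. The case for correction rests on clear dosing instructions and patient safety. No view is taken here on which rule is clinically right.

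**What to change.** Reconcile sections 6.1.2.2 and 6.3.1.16.1 so that one instruction applies to each situation:

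1. State which drug or drugs the low-count hold covers within a cycle, and make the closing vincristine line agree with it.
2. State the same for the start of a cycle, including cycles 2 to 8 when counts have not recovered.
3. State which sentence governs carboplatin at the next maintenance cycle after a reduction, and word the full-dose sentence to match.

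The sponsor and steering committee settle the clinical content, and the result goes to all sites as a single clarification. The cost is wording in a protocol clarification or amendment, with no extra patients, visits or procedures.
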